#### **6.3.2.6 Height and Weight**

The analysis of height and weight will be summarized at each timepoint, presenting descriptive statistics for both.

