This is a multicenter, open-label extension of Study 109MS202 that is designed to evaluate the long-term safety and efficacy of BG00012 in pediatric subjects.

Study Location:

Approximately 20 sites globally are planned.

Number of Planned Subjects:

The number of subjects who are eligible for this study will be determined by the number of subjects who have completed Study 109MS202 as per protocol.

Study Population:

This study will be conducted in subjects who completed Study 109MS202 as per protocol.

Detailed criteria are described in Section 8.

Treatment Groups:

All subjects will receive BG00012 240 mg twice daily (2 capsules of 120 mg).

Duration of Treatment and Follow-up:

The treatment period is 96 weeks (2 years) and the Follow-Up Safety Visit will take place 4 weeks after the last dose of study treatment.

[figure not shown]
CONFIDENTIAL

The information contained herein may not be used, disclosed, or published without the written consent of Biogen MA Inc.

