5.5. Rationale for Dosing Regimen

The BG00012 dosage selected for this study (240 mg BID) is the approved BG00012 dosing regimen in adult patients with MS.

In adults, after oral administration, DMF is well absorbed and extensively metabolized by esterases to its primary active metabolite, monomethyl fumarate (MMF). As a result, DMF is not quantifiable in plasma, and all PK analyses have been performed based on MMF concentrations. Downstream metabolism of DMF/MMF occurs through the tricarboxylic acid cycle, with exhalation of carbon dioxide serving as a major route of elimination. The PK of BG00012 has been thoroughly evaluated in adults. Body weight is a significant covariant for BG00012 exposure in that the area under the curve and the maximum concentration are decreased by 2% and 1.4%, respectively, for every 1-kg increase in body weight within the weight range of 45 to 112 kg. This translates to a 2-fold increase in exposure levels as body weight decreases from 112 to 45 kg.

Despite the effect of body weight changes on the exposure levels of BG00012, data from the pivotal Phase 3 studies suggested that the variability in exposure did not affect safety and efficacy measures in adult patients. Notably, the efficacy and tolerability profiles of BG00012 at 240 mg BID were indistinguishable from those at 240 mg TID, with a wide range of overlapping exposures between the 2 dosages.

A Phase 1 PK study (Study 109MS101) revealed no apparent differences in the kinetics of BG00012 across the age range of 21 to 51 years once the weight relationship was accounted for.

Published data [Zhu 2009] indicate that there were no notable differences in the expression and activities of esterases in juveniles (12 to 18 years old) when compared with adults. These findings suggest that the disposition of BG00012 is unlikely to change with age for the target population (10 to 18 year olds).

Taken together, these data indicate that 240 mg BID, the approved dose in adults, should be tolerable in pediatric subjects meeting the inclusion criteria for the parent study (109MS202) and the current extension study. As such, this dose was chosen for the parent and current studies.

CONFIDENTIAL

The information contained herein may not be used, disclosed, or published without the written consent of Biogen MA Inc.

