## **5 SAMPLE SIZE JUSTIFICATION**

Because this study is an extension study, the sample size was determined by the number of eligible subjects who completed Study 109MS202.

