## **6 STATISTICAL ANALYSIS METHODS**

The statistical software, SAS®, will be used for all summaries and statistical analyses.

Statistical analyses will be descriptive in nature with appropriate measures of variation provided where applicable. For continuous endpoints, summary statistics will generally include the following: number of subjects with data, mean, standard deviation, median, and range. For categorical endpoints, summary statistics will generally include the frequency distribution of the analysis population.

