### **6.1 Description of Analytic Methods**

As the study contains a single treatment group, descriptive statistics will be the primary approach to analyze the data.

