#### **6.1.4 Demographic and Baseline Characteristics**

Demographic data, including age (in years, at the time of consent to study 109MS311), gender and race category will be summarized for the subjects that enroll into study 109MS311. In addition, baseline height (cm) and weight (kg) will also be presented.

Medical history will be summarized for just those subjects who enrolled in 109MS311 by category using number and percentage of subjects that had experienced certain maladies prior to entering the study. Medical history will include information collected in 109MS202, but for only those subjects who entered 109MS311. Included will be the number of subjects with ongoing or resolved medical/surgical history that have occurred since the subject enrolled in 109MS202.

The MS Pediatric Diagnostic Criteria as defined by Krupp (2013), obtained at screening of study 109MS202, will be summarized for those subjects who enrolled into 109MS311.

MS signs considered typical MS signs and symptoms will be summarized for each area: vision, cognition, coordination/balance, bladder control, bowel, sexual function, and general. In addition, MS signs related to sensory disturbances, motor disturbances, and other will be presented for the population and summarized. Only those subjects who entered 109MS311 will be included in the summaries.

History of MS for the subjects enrolled in 109MS311 will be summarized using information collected prior to study 109MS202. This includes time since first MS diagnosis, time since first symptoms, number of relapses prior to screening in study 109MS202 (prior 12 months, 2 years, and 3 years) and the time since the last relapse prior to 109MS202. In addition, the MS treatment history will be summarized for these subjects in 109MS311 prior to receiving BG00012 in the 109MS202 study.

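### Height and weight are tabulated only as unstandardised values by visit, which in one arm of growing subjects cannot separate expected growth or a change in age mix from a moderate growth deficit

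*SAP*

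**What the plan says.** SAP 6.3.2.6 is the whole plan for growth: "The analysis of height and weight will be summarized at each timepoint, presenting descriptive statistics for both". SAP section 6 says what descriptive statistics generally means for a continuous variable: "number of subjects with data, mean, standard deviation, median, and range".

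Change from baseline is specified for laboratory values (SAP 6.3.2.3) and vital signs (SAP 6.3.2.4), and vital signs also have a table of abnormality criteria. Height and weight have neither. Neither document mentions z-scores, percentiles, growth velocity, a growth reference, pubertal stage or a criterion for abnormal growth.

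Protocol 14.1 lists body weight and height among the clinical safety assessments. The schedule takes height at baseline, Weeks 24, 48, 72 and 96 and the safety follow-up, and weight more often. Protocol 5.5 gives the target population as 10 to 18 years, and the Synopsis gives 96 weeks of treatment. On design, SAP 6.1 states: "As the study contains a single treatment group, descriptive statistics will be the primary approach to analyze the data". SAP 6.1.4 shows that the variables needed for standardisation are held: "age (in years, at the time of consent to study 109MS311), gender and race category will be summarized".

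**The concern.** A visit mean of raw height in this age range contains three things: the growth these subjects would have had anyway, any shortfall from it, and the ages of those measured at that visit. With a control arm, the first and third would largely cancel in the comparison. Here there is no control arm, and the plan supplies no external yardstick in its place. A rising mean will look reassuring whether or not growth is slower than it should be.

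Change from baseline alone would deal with the shifting age mix among those measured, but it would still leave expected growth unknown, because that depends on age and sex.

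The primary objective is long-term safety in pediatric subjects, and height and weight are measured repeatedly for that purpose. As planned, the tables do not let a reader judge whether growth was normal.

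**Working it through.** The plan has no figure to reproduce. It states no growth rate, no deficit of interest and no SD, and gives no number of subjects: "the sample size was determined by the number of eligible subjects who completed Study 109MS202". What follows illustrates the mechanism for height.

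**From the documents.** Treatment lasts 96 weeks: 96 × 7 / 365.25 = 1.84 years. One arm. Target age 10 to 18 years.

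**Assumed, not in the documents.** Mean growth g = 2, 3 or 5 cm/yr; deficit d = 0.25, 0.5 or 1.0 cm/yr; SD of raw height across subjects 8 to 14 cm; 7 cm per 1 z; SD of the 96-week change in z, s = 0.3 to 0.5; N = 10, 20 or 40.

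**Step 1. What the raw mean does.** Mean change = (g − d) × 1.84.

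| g (cm/yr) | no deficit | d = 1 cm/yr |
|---|---|---|
| 2 | 3.68 cm | 1.84 cm |
| 3 | 5.52 cm | 3.68 cm |
| 5 | 9.20 cm | 7.36 cm |

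The mean rises in every cell. A gain of 3.68 cm is normal growth if g = 2 and a 1 cm/yr deficit if g = 3; the planned table cannot say which. Only when d approaches g does the gain approach zero and the problem become plain.

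**Step 2. Precision shown.** SE of a visit mean = SD/√N: 2.5 to 4.4 cm at N = 10, 1.8 to 3.1 cm at N = 20, 1.3 to 2.2 cm at N = 40. The 1.84 cm deficit is below or close to these at N = 10 and 20. If the same subjects attend both visits, subtracting the two means does remove the between-subject spread, but the planned statistics give no SD for that difference.

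**Step 3. Change in who is measured.** If 4 of 20 subjects, averaging 15 cm shorter than the other 16, leave, the mean rises by (4/20) × 15 = 3 cm with no growth at all.

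**Step 4. Standardised change.** If subjects grow as the reference does, mean within-subject change in z is near 0. A deficit shifts it by −d × 1.84 / 7. The chance that the mean change differs from 0 at two-sided 5% is Φ(|shift| / (s/√N) − 1.96), a normal approximation that is somewhat optimistic at N = 10. For d = 1.0, N = 20, s = 0.5: 0.263 / 0.112 = 2.35; 2.35 − 1.96 = 0.39; Φ = 65%.

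| d (cm/yr) | shift in z | N = 10 | N = 20 | N = 40 |
|---|---|---|---|---|
| 1.0 | −0.26 | 38–79% | 65–97% | 91–100% |
| 0.5 | −0.13 | 13–28% | 22–50% | 38–79% |
| 0.25 | −0.07 | 6–10% | 8–16% | 13–28% |

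Ranges run from s = 0.5 to s = 0.3.

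**Step 5. Subjects who have stopped growing.** They cannot lose height score through slowed growth. If they are half the sample, −0.26 becomes 0.5 × (−0.26) = −0.13. With s unchanged, the chance falls to the second row: 22–50% at N = 20 and 13–28% at N = 10.

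**The case against.** Growth is not an objective or endpoint in either document, and the background sections of the protocol report no growth signal. The analysis is descriptive throughout, so little turns on prespecification; standardised scores could be derived later from the same data. Clinically evident growth failure or weight loss could be recorded as an adverse event and so reach the primary endpoint. The age range comes from the dosing rationale, while the extension's own eligibility criteria set no age limits, so the share of subjects still growing is unknown. Every centimetre figure above is assumed.

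Much of this stands, and it limits the importance of the point. It does not make the planned tables readable: adverse event capture depends on an investigator noticing a gradual shortfall, and an analysis that can be done later is not one that is planned.

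A reader might also infer three stronger things:

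- That raw means hide any effect on growth. They do not: growth arrest or marked weight loss could show.
- That standardised scores would reveal a treatment effect. With one arm they show departure from a reference population. The disease, steroid courses for relapse (Protocol 11.5.3) and pubertal timing can all produce it.
- That the mean score change is unaffected by age mix. Under normal growth it is near 0 at any mix, but the size of a shift under slowed growth depends on how many subjects are still growing (Step 5).

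**Conclusion.** The point holds as a gap in the analysis of safety data already being collected. Followed as written, SAP 6.3.2.6 yields tables in which a moderate growth deficit cannot be told from expected growth or from a change in who attends, and nothing elsewhere in either document supplies the missing yardstick. A very large effect could still be seen.

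The size is illustrative only. At 2 to 5 cm/yr, a 1 cm/yr deficit leaves the raw mean rising 1.8 to 7.4 cm, while the standardised change would shift by about −0.26 z. Smaller shifts would often be missed at 10 to 20 subjects even with the better analysis, and subjects at or near final height add little to the height result.

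The baseline sets one further limit. Subjects enter already on BG00012 (Protocol 8.1, criterion 2), and baseline is Day 1 of 109MS311 (SAP 6.1.1). Change from that baseline alone would miss any effect that arose in the parent study.

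**What to change.** In SAP 6.3.2.6, keep the raw tables and add:

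1. Age- and sex-standardised height and weight scores at each visit (BMI optional), from one growth reference named in advance, with a stated rule for subjects above its upper age. A subject aged 18 at entry would be about 18 + 1.84 = 19.8 years at Week 96.
2. Within-subject change in score with a confidence interval, from the 109MS311 baseline and, if available, from the pre-treatment 109MS202 value. SAP 6.1.1 already draws on 109MS202 baseline demographics for these subjects.
3. The number and a listing of subjects whose score falls by more than an amount set in advance.
4. A sentence stating that the result is departure from the reference population and not a causal drug effect, that small shifts may be missed at small N, and that subjects at or near final height contribute little to the height result.

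No new visit or measurement is needed. Age at each visit has to be derived, which should be possible because SAP 6.1.1 already recalculates age at consent. The cost is SAP wording, a little programming and the choice of one reference for a multinational sample.
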